7.1.3. Packaging and Labeling

All study drug will be provided by Lilly. Clinical study materials will be labeled according to the country's regulatory requirements.

7.2. Method of Treatment Assignment

Patients who meet all criteria for enrollment will be assigned to receive LY3405105 in this study. The Sponsor will confirm the dose and identification number assignment and dose level for each patient. No dose escalations (that is, to the next dose level) can occur without prior discussion and agreement with Lilly.

If investigators have eligible patients who have consented concurrently, more than the assigned number of patients may be entered at a particular dose level provided that accrual has not ceased due to excessive toxicity. This enrollment procedure is allowed because of the advanced disease state of this patient population and the screening involved in defining eligibility. This event should be approved by the Sponsor following discussions with the investigators.

7.2.1. Selection and Timing of Doses

The dosing cycle is defined as an interval of 28 days. During the monotherapy dose escalation, patients will receive doses once daily starting on Day 1 through Day 28 of a 28-day cycle. For visits where PK samples will be collected, patients are required to take the morning dose of LY3405105 at the hospital/clinic (not at home) after the predose PK sample collection has occurred.

LY3405105 will be administered on an empty stomach (meals should not be consumed within 1 hour either side of dosing). Doses should be taken approximately the same time each day (± 2 hours) as much as possible. If a patient misses or vomits a dose, that dose should be omitted. Patients must record the time and amount of each dose taken (or alternatively, the time and amount of the dose missed or vomited) in a daily diary.

A delay of a cycle due to holiday, weekend, bad weather, or other unforeseen circumstances will be permitted for a maximum of 7 days and not counted as a protocol deviation. The reason for interruption should be documented on the electronic case report form (eCRF).

A patient may continue to receive study treatment until confirmed progressive disease (Section 9.1), unacceptable toxicity, or discontinuation for any other reason (Section 8). Patients with documented progressive disease may be allowed to continue LY3405105 if the patient is tolerating treatment and, in the opinion of the investigator, is deriving clinical benefit from continuing study treatment and continuation of treatment is approved by the Sponsor.

7.3. Blinding

This is an open-label study.

7.4. Dose Modification

Doses of the study drugs may need to be delayed, reduced, or discontinued to manage specific AEs or other toxicities. Investigators should review the relationship of an AE to the study drug to determine if study drug requires dose adjustment or delay ([Table JZFA.7.2](#)).

When a study drug is delayed, if possible and appropriate, patients should resume study treatment within 1 treatment cycle and, if not possible, then every effort should be made to start on the first day of the next dosing cycle. In rare circumstances, a delay >28 days may be permitted before permanent treatment discontinuation, as long as the patient has clinical benefit without objective disease progression and is recovering from the toxicity. Such circumstances must be discussed with Lilly. All dose modifications should be documented, including the approach taken, and a clear rationale for the need for modification.

Any patient who requires a dose reduction will continue to receive the reduced dose for the remainder of the study. Any patient who has had 2 dose reductions and who experiences a toxicity that would cause a third dose reduction must be discontinued from study treatment.

If the patient is in Cycle 6 or beyond and is continuing to receive benefit from therapy, additional delays may be acceptable if agreed upon by both the investigator and the Sponsor. If a patient has a non-drug-related AE (for example, pneumonia or prolonged flu) requiring a delay of more than 1 week, the patient may continue on therapy if, in the opinion of the investigator, he/she is showing benefit from therapy and has recovered sufficiently from the AE. Additional procedures may be required for delayed patients before resuming treatment.

Table JZFA.7.2. Dose Modifications in Patients due to Toxicity

Toxicity Type	Toxicity Profile and Severity	Dose Suspension	Dose Reduction
Hematologic toxicity	Grade 3	Dose MUST be suspended until toxicity resolves to at least Grade 2.	Dose MAY be reduced by 1 dose level at the investigator's discretion.
Hematologic toxicity	Recurrent Grade 3	Dose MUST be suspended until toxicity resolves to at least Grade 2.	Dose MUST be reduced by 1 dose level.
Hematologic toxicity	Grade 4	Dose MUST be suspended until toxicity resolves to at least Grade 2.	Dose MUST be reduced by 1 dose level.
Hematologic toxicity: Patient requires administration of blood cell growth factors	Regardless of severity. Growth factors use according to ASCO guidelines	Dose MUST be suspended for at least 48 hours after the last dose of blood cell growth factors was administered and until toxicity resolves to at least Grade 2.	Dose MUST be reduced by 1 dose level unless already performed for incidence of toxicity that lead to the use of growth factor.
Nonhematologic toxicity (except diarrhea)	Persistent or recurrent Grade 2 that does not resolve with maximal supportive measures within 7 days to baseline or Grade 1	Dose MAY be suspended until toxicity resolves to either baseline or Grade 1.	Dose MAY be reduced by 1 dose level – investigator's discretion.
Nonhematologic toxicity	Grade 3 or 4 that does not resolve with maximal supportive measures within 72 hours to baseline or Grade 1	Dose MUST be suspended until toxicity resolves to either baseline or Grade 1.	Dose MUST be reduced by 1 dose level.
Diarrhea	Requires hospitalization for Grade 3 or 4	Dose MUST be suspended until toxicity resolves to at least Grade 1.	Dose MUST be reduced by 1 dose level.
Diarrhea	Persistent or recurrent Grade 2 that does not resolve with maximal supportive measures within 24 hours to at least Grade 1	Dose MUST be suspended until toxicity resolves to at least Grade 1.	Dose MAY be reduced by 1 dose level – investigator's discretion.
Diarrhea	Persistent or recurrent Grade 1 that does not resolve with maximal supportive measures within 24 hours to baseline	Patient to be followed for 48 hours to ensure grade does not worsen.	Dose MAY be maintained during monitoring – investigator's discretion.
Diarrhea	Diarrhea recurs despite maximal supportive measures after resuming same dose level after initial Grade 2 diarrhea	Dose MUST be suspended until toxicity resolves to at least Grade 1.	Dose MUST be reduced by 1 dose level.
Bloody diarrhea	Any grade	Dose MUST be suspended until bloody diarrhea resolves and diarrhea resolves to at least Grade 1.	Dose MUST be reduced by 1 dose level.
Nonhematologic toxicity (laboratory)	Total bilirubin $>2 \times$ ULN with ALT/AST $>3 \times$ ULN in the absence of cholestasis	Dose MUST be permanently suspended.	Dose MUST be permanently suspended.
Nonhematologic toxicity (vital organs of clinical concern, for example cardiotoxicity, pneumonitis, neurotoxicity)	Grade 2	Dose MUST be suspended until toxicity resolves to either baseline or Grade 1. If not resolved to Grade 1 within around 14 days, discussion between the investigator and Lilly CRP is recommended.	Dose MAY be reduced by 1 dose level – investigator's discretion.

Abbreviation: ALT = alanine aminotransferase; ASCO = American Society of Clinical Oncology; AST = aspartate aminotransferase; MAY = per the investigator's clinical judgment; MUST = mandatory; ULN = upper limit of normal

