7.1.1.1. Dose-Limiting Toxicity Determination and Maximum Tolerated Dose Definition

Dose-limiting toxicity is defined as a clinically significant AE during Cycle 1 of the dose escalation phase that is possibly related to LY3405105 during Phase 1a and fulfills any one of the following criteria using the National Cancer Institute's Common Terminology Criteria for Adverse Events (CTCAE) v4.0:

- \geq CTCAE Grade 3 non-hematological toxicity. Exceptions will be made for:
 - Grade 3 nausea or constipation that lasts for <72 hours and can be controlled with treatment
 - Grade 3 diarrhea, vomiting, or electrolyte disturbance that lasts for <72 hours and can be controlled with treatment
 - fatigue or anorexia. Grade 3 or Grade 4 fatigue should be considered a DLT if persisting >5 days
 - Transient Grade 3 elevations of alanine aminotransferase (ALT) and/or aspartate aminotransferase (AST), without evidence of other hepatic injury, in the setting of preexisting hepatic metastasis and baseline elevation of these values may not be considered a DLT if agreed by the study investigator and Lilly CRP/CRS.

- Total bilirubin $>2 \times$ upper limit of normal (ULN) with ALT/AST $>3 \times$ ULN in the absence of cholestasis (alkaline phosphatase $<2 \times$ ULN)
- Grade 4 neutropenia >5 days duration
- any febrile neutropenia
- Grade 4 thrombocytopenia of any duration
- Grade 3 thrombocytopenia with clinically significant bleeding
- Grade 3/4 anemia
- any other significant toxicity deemed by the primary investigator and Lilly to be dose limiting (for example, any toxicity that is possibly related to the study medication that requires the withdrawal of the patient from the study during Cycle 1 or certain Grade 2 AEs affecting vital organs)
 - A DLT-equivalent toxicity is defined as an AE occurring after Cycle 1 for a patient enrolled in Phase 1a. It will also apply to patients treated in any cycle in Phase 1b (including Cycle 1) that would have met the criteria for DLT.

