8.1. Discontinuation from Study Treatment

Patients will be discontinued from study treatment in the following circumstances:

- the patient is enrolled in any other clinical study involving an investigational product or any other type of medical research judged not to be scientifically or medically compatible with this study
- the patient becomes pregnant during the study
- the patient is significantly noncompliant with study procedures and/or treatment as described in Section 7.6
- the patient has confirmed progressive disease

Exception: Patients with documented progressive disease may be allowed to continue LY3405105 if the patient is tolerating treatment and, in the opinion of the investigator, is deriving clinical benefit from continuing study treatment and continuation of treatment is approved by the Sponsor.

- the patient experiences unacceptable toxicity
- the patient has had 2 dose reductions and experiences an AE that would cause a third dose reduction
- the investigator decides that the patient should be discontinued from study treatment
- the patient requests to be discontinued from study treatment
- the patient's legal representative requests that the patient be discontinued from study treatment.

Patients who are discontinued from study treatment will have follow-up procedures performed as shown in the Schedule of Activities (Section 2).

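### Table JZFA.7.2 requires an immediate hold for vital-organ toxicity at Grade 2, but for an event first seen at Grade 3 or 4 only after 72 hours without resolution

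*Protocol*

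**What the plan says.** Two rows of Table JZFA.7.2 (Protocol Section 7.4) matter here.

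- **Vital-organ row.** It covers "vital organs of clinical concern, for example cardiotoxicity, pneumonitis, neurotoxicity". Its severity cell names Grade 2 and nothing else. The suspension cell begins "Dose MUST be suspended until toxicity resolves to either baseline or Grade 1. If not resolved to Grade 1 within around 14 days", after which it recommends a discussion with the sponsor's physician. Reduction by one dose level is optional.
- **General nonhematologic row.** Its severity cell reads "Grade 3 or 4 that does not resolve with maximal supportive measures within 72 hours to baseline or Grade 1". When that condition is met, both suspension and a one-level reduction are mandatory.

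The table's footnote defines MUST as mandatory and MAY as the investigator's judgment.

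The DLT definition in Section 7.1.1.1 gives context. After its ≥ sign the criterion reads "CTCAE Grade 3 non-hematological toxicity. Exceptions will be made for", followed by a list. One listed exception is "Grade 3 diarrhea, vomiting, or electrolyte disturbance that lasts for <72 hours and can be controlled with treatment"; nausea and constipation have a similar 72-hour tolerance. No exception names cardiac, lung or nerve toxicity. The same section gives "certain Grade 2 AEs affecting vital organs" as an example of what may be judged dose limiting.

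**The concern.** A table of mandatory actions sets the least that every site must do, and that minimum should not loosen as toxicity worsens. For vital organs it does. Grade 2 has an immediate required hold, while a new Grade 3 or 4 event has none for up to 72 hours.

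First detection above Grade 2 is plausible. In Phase 1b the only scheduled ECG is at baseline (Table JZFA.2.2), and from Cycle 3 scheduled visits fall on Day 1 of each 28-day cycle. At stake is the protection of individual patients; no endpoint or analysis depends on this table.

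**Working it through.** There is no planned figure to reproduce. The check sets the rows side by side, then looks for any other text that requires a hold.

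**Step 1. When does a hold become mandatory?**

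| Event | Row that applies | Required hold | Reduction |
|---|---|---|---|
| Vital organ, Grade 2 | Vital-organ row | At once | Optional |
| Vital organ, first seen at Grade 3-4, not at baseline or Grade 1 by 72 h | General row | At 72 h | Mandatory |
| Vital organ, first seen at Grade 3-4, falls to Grade 2 before 72 h | Vital-organ row from the fall | At the fall | Optional then; mandatory if not at baseline or Grade 1 by 72 h |
| Vital organ, first seen at Grade 3-4, at baseline or Grade 1 within 72 h, no Grade 2 stage observed | General row, condition not met | None | None |
| Hematologic, Grade 3 or 4 (comparison) | Hematologic rows | At once | Optional at first Grade 3; mandatory at recurrent Grade 3 and at Grade 4 |

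A patient already held at Grade 2 who worsens stays held. Liver injury meeting the combined bilirubin and ALT/AST row is permanently suspended with no wait, so it lies outside the gap.

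**Step 2. How many doses fall in the window?** Dosing is once daily (Section 7.2.1), so doses = window in hours / 24.

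- Grade 2: 0/24 = 0 doses.
- Grade 3-4 falling to Grade 2 at 24 h or 48 h: 24/24 = 1 or 48/24 = 2 doses.
- Grade 3-4 for the full window: 72/24 = 3 doses.

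Section 7.2.1 lets each dose move by 2 hours either way. Four consecutive doses nominally span 72 h, so the span can be as short as 72 − 4 = 68 h or as long as 72 + 4 = 76 h. A 72-hour window can therefore hold 2 to 4 doses, with 3 as the central value.

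**Step 3. When does the clock start?** The row does not say whether the 72 hours run from onset or recognition. From recognition, the full window applies. From onset, an event found more than 72 hours later already meets the mandatory row, and no window is left at detection.

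**Step 4. Does other text require a hold?**

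- Section 7.4, text: "Investigators should review the relationship of an AE to the study drug to determine if study drug requires dose adjustment or delay". This asks for judgment.
- Section 7.1.1.1: classifies events as dose limiting and orders no hold.
- Section 7.1.2: Grade 4 toxicity not clearly due to other causes prompts a review and stops accrual. It does not address the affected patient's dosing.
- Section 8.1: treatment stops when "the patient experiences unacceptable toxicity", with no grade or timing given.
- Section 9.2.1: serious events must be notified within 24 hours; no hold is attached.
- Section 9.4.2: repeat liver tests and monitoring only.

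None supplies a required hold for a Grade 3-4 cardiac, lung or nerve event before 72 hours.

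**The case against.** The strongest reply is that this is a drafting gap which no competent investigator would exploit. A clinician would read Grade 2 as the entry threshold. The general row presupposes full supportive care. Section 9.2 makes investigators responsible for appropriate medical care, and Section 8.1 lets them stop treatment at any time. Serious events reach the sponsor within 24 hours, well inside the window. Late discovery may also leave no window if the clock runs from onset.

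Most of this stands, and it limits the weight of the point. It does not change the required minimum. The threshold reading is not what the row says. The table writes ranges elsewhere when it means them (Grade 3 or 4, any grade, regardless of severity). Extending the row as it stands to Grade 3-4 would also set an optional reduction against the general row's mandatory one.

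Three stronger readings are tempting, and the documents support none of them.

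- **That the protocol directs dosing through a Grade 3-4 vital-organ event.** It does not; it only fails to forbid it for up to 72 hours.
- **That the whole table runs backwards.** Reduction does not: it is mandatory at Grade 3-4 once the 72-hour condition is met, and optional at Grade 2. Nor is diarrhea part of the point, because the DLT exceptions share the 72-hour tolerance for controlled Grade 3 diarrhea.
- **That nonclinical findings show a specific hazard.** Section 3.2.2 lists decreased heart rate but considers it monitorable and/or manageable, names gut and bone marrow effects as the key toxicities, and lists no lung or nerve finding.

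**Conclusion.** The point holds as a defect in the mandatory minimum. For a vital-organ event first seen at Grade 3 or 4, the required hold can come up to 72 hours later than for one at Grade 2, a span of about 3 once-daily doses. That figure is an upper case. It assumes that the clock starts at onset or recognition with the full 72 hours ahead, that the event does not pass through Grade 2, and that the investigator does not hold sooner. Investigators probably would hold sooner. Because the documents give no rate for such events, the number of patients affected cannot be computed. The defect is worth correcting because it concerns patient safety and the remedy is confined to one table row.

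**What to change.** In the vital-organ row, change the severity cell from Grade 2 to Grade 2 or higher for immediate mandatory suspension. In its reduction cell, keep the optional reduction for Grade 2 and, for Grade 3 or 4, refer to the general nonhematologic row. The mandatory one-level reduction then still applies only when the event has not resolved within 72 hours. Leave the general row as it is.

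This needs new wording in one row, by amendment or clarification letter. The downside is a few more short interruptions, including for Grade 3 events that would have settled within 72 hours.

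The reduction should stay conditional. Under Section 7.4 a reduced dose is kept for the rest of the study, and a toxicity that would call for a third reduction ends treatment. Whether Grade 3-4 vital-organ events should carry an unconditional reduction or discontinuation is a separate clinical decision and is not part of this change.

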7.5. Preparation/Handling/Storage/Accountability

LY3405105 capsules/tablets for oral consumption will be supplied by Lilly and labeled according to country regulation requirements. All study treatment should be stored according to their associated product label and taken as directed. Patients should store all study treatment in the original package provided according to the product label and be instructed to keep all medications out of reach from children. Capsules/tablets should not be opened, crushed, or dissolved.

7.6. Treatment Compliance

Patient compliance with study drug will be assessed at each visit. LY3405105 compliance will be assessed by direct questioning, counting returned capsules/tablets/packages, and reviewing patient diaries. Deviations from the prescribed dosage regimen should be recorded on the CRF.

A patient will be considered significantly noncompliant if he/she misses more than 20% cumulative days of study medication (full doses) during each cycle. A patient may be considered significantly noncompliant if he or she is judged by the investigator to have intentionally or repeatedly taken more than the prescribed amount of medication.

7.6.1. **Evaluable Patients**

Patients who withdraw from the study before receiving study drug(s) will be replaced and will not be included in the safety or efficacy assessments. Safety analyses will be conducted on all patients who have received at least 1 dose of study drug, regardless of whether they are deemed evaluable for the assessment of a dose level.

Any patient who is discontinued from the study before receiving at least 80% of LY3405105 planned doses in Cycle 1 will be deemed non-evaluable for assessment of safety at that dose level and may be replaced unless they experience a DLT or dose omission/reduction due to toxicity prior to withdrawal. A patient may be deemed non-evaluable for assessment of a dose level in the event the patient experiences an AE which would meet DLT criteria, and furthermore has been determined through discussion between investigator and Lilly CRP/CRS to most likely be related to a concomitant medication or a prior line of immune therapy (in the case of immune-related AEs) due to previously established linkage.

If the patient is noncompliant during Cycle 1 due to reasons other than drug-related toxicity, he or she will be considered non-evaluable and may be replaced.

Non-evaluable patients may be replaced to ensure that at least 3 patients complete 1 cycle of therapy at each dose level, unless accrual to that dose level has stopped due to a DLT.

Patients who are not evaluable for PK, but who complete 1 cycle of therapy, may be replaced upon consultation with the investigator(s) and the Lilly CRP/CRS to ensure adequate PK data, unless accrual to that dose level has stopped due to a DLT.

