Appendix 7. Statistical Details for Dose Escalation

Dose escalation will be driven by safety. A model-based method that incorporates prior expectations about the dose-toxicity curve and controls for over-dosing probability will be applied to the data at the end of each dose level, which will provide quantitative guidance to the investigators and Lilly CRP to help determine the next dose level.

The model to be utilized is a two-parameter logistic model (Neuenschwander et al. 2008). For example, the 2 parameters follow a bivariate normal distribution with minimally informative prior distribution, $\mu_1=-3.88$, $\mu_2=-0.11$, $\sigma_1=2.85$, $\sigma_2=0.17$, $\rho=-0.88$ if the prior parameters are set such that the median probability of DLT at the 1 mg dose is 0.01 (95% CrI 0.0 to 0.85), and the median probability of DLT at the 30 mg dose is 0.28 (95% CrI 0.0 to 0.95). In the logistic model, the reference dose is set at dose level 1 (1 mg).

The posterior probability of a DLT at each dose level will be categorized to 4 bands, defined as:

- Under-dosing: the probability of a DLT at a given dose level in (0, 0.20)
- Targeted toxicity: the probability of a DLT at a given dose level in (0.20, 0.33)
- Excessive toxicity: the probability of a DLT at a given dose level in (0.33, 0.60)
- Unacceptable toxicity: the probability of a DLT at a given dose level in (0.60, 1.00)

The model aims to recommend a dose which maximizes the probability of targeted toxicity, while controlling the probability of excessive or unacceptable toxicity to less than 25% and controlling the probability of unacceptable toxicity to less than 5%. The probability of excessive or unacceptable toxicity is changed to 40% after Cohort 8. The maximum increment of escalation will be no more than 100%. The exact increment will be determined by the investigators and Lilly CRP/CRS and may be less than the model prediction or <100%.

Simulations were conducted using FACTs v6.0 to verify the operating characteristics of the model-based dose escalation. Three scenarios were considered with varying DLT rates across the dose range, representing 3 different toxicity profiles, where Scenario 2 is the same as the prior probabilities used to derive the bivariate normal distribution used in the 2-parameter logistic model.

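### Phase 1a early leavers with any toxicity-related dose omission or reduction stay evaluable with no minimum exposure or follow-up, so by inference the N-CRM counts those without a DLT as full non-DLTs

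*Protocol*

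**What the plan says.** Protocol 7.6.1 sets the threshold: "Any patient who is discontinued from the study before receiving at least 80% of LY3405105 planned doses in Cycle 1 will be deemed non-evaluable". This concerns the safety assessment at the patient's dose level. It adds that the patient "may be replaced unless they experience a DLT or dose omission/reduction due to toxicity prior to withdrawal". One *unless* covers both exceptions. DLT patients plainly have to count, so the natural reading is that patients with a toxicity-related omission or reduction stay evaluable too. No grade, number of doses, minimum follow-up or reason for leaving is attached.

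Two other statements in 7.6.1 bear on this. First, a patient whose Cycle 1 noncompliance has a cause other than drug toxicity is non-evaluable and replaceable. Second, "Non-evaluable patients may be replaced to ensure that at least 3 patients complete 1 cycle of therapy at each dose level".

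On outcome, 7.1.1.1 says: "Dose-limiting toxicity is defined as a clinically significant AE during Cycle 1 of the dose escalation phase". Its catch-all criterion lets the investigator and sponsor agree to class other toxicities as DLTs; one case it names is "any toxicity that is possibly related to the study medication that requires the withdrawal of the patient from the study during Cycle 1".

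Appendix 7 fits a two-parameter logistic model and describes no weighting for partial follow-up. It aims at the targeted toxicity band while "controlling the probability of excessive or unacceptable toxicity to less than 25"%, and unacceptable toxicity to less than 5%. Section 7.1.1.2 makes the model's recommendation a ceiling on dose. Neither protocol 10.2 nor the SAP defines a DLT-evaluable population. SAP 6.3 counts a Phase 1a patient as completing if evaluable for DLT.

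**The concern.** The exception looks designed to stop patients with toxicity from dropping out of the dose assessment. In a yes/no model it can do the opposite. A patient with a toxicity below DLT severity, who then leaves with little exposure, becomes full evidence that the dose was tolerated.

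The trigger is realistic. Table JZFA.7.2 allows or requires suspension for events that are not listed DLTs. Grade 3 hematologic toxicity must be suspended, yet Grade 3 neutropenia without fever is not on the DLT list. For persistent or recurrent Grade 2 nonhematologic toxicity, "Dose MAY be suspended until toxicity resolves to either baseline or Grade 1". Such a patient may then leave for progression or withdrawn consent.

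At stake are the DLT estimate behind the MTD and RP2D, and the overdose limit protecting the next patients. Because only non-evaluable patients may be replaced, a three-patient level could also be judged on two who completed the cycle, against the stated aim of three.

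**Working it through.** **Exposure threshold.** Section 7.2.1: "patients will receive doses once daily starting on Day 1 through Day 28 of a 28-day cycle". Then 0.80 × 28 = 22.4, so 23 doses are needed. A patient who omits one dose and leaves on Day 6 has had about 5 of 28 doses (18%).

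**Model.** logit p(d) = a + exp(b) × log(d / 1 mg), with (a, b) bivariate normal: means −3.88 and −0.11, SDs 2.85 and 0.17, correlation −0.88 (Appendix 7). The posterior comes from a binomial likelihood at each dose, integrated on a grid.

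**The plan's own figures first (prior median and 95% CrI).**

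| Dose | Appendix 7 | Recomputed |
|---|---|---|
| 1 mg | 0.01 (0.0 to 0.85) | 0.020 (0.0001 to 0.847) |
| 30 mg | 0.28 (0.0 to 0.95) | 0.306 (0.0045 to 0.982) |

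The match is close but not exact, and Appendix 7 offers the prior as an example. The results below are therefore illustrations.

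**Four enrolled, one DLT, one early leaver.** Assume 0/3 DLTs at every lower level of Table JZFA.7.1. Leaving the early leaver out gives 1/3; counting the patient as a full non-DLT gives 1/4. The table shows P(DLT rate >0.33) at the next dose.

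| Step | 1/3 | 1/4 | Against the limits |
|---|---|---|---|
| 1 to 2 mg | 0.437 | 0.334 | blocked both ways |
| 2 to 4 mg | 0.287 | 0.226 | blocked, then allowed |
| 4 to 8 mg | 0.247 | 0.197 | allowed both ways |
| 8 to 15 mg | 0.228 | 0.183 | allowed both ways |
| 15 to 30 mg | 0.260 | 0.213 | blocked, then allowed |
| 30 to 45 mg | 0.203 | 0.159 | allowed both ways |

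In the two steps that flip, P(DLT rate >0.60) is at most 0.040, so the 25% limit decides. At 15 mg with 1/4, the target-band (0.20 to 0.33) probability is 0.276 at 30 mg against 0.176 at 15 mg, so the model would then prefer 30 mg.

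**No DLT at the level.** The next example dose is allowed whether or not the early leaver counts. For 15 to 30 mg, 0/3 gives 0.042 and 0/4 gives 0.032.

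**Credit in proportion to exposure.** Let the early leaver contribute (1 − p)^w. For 15 to 30 mg, w = 0 gives 0.260, w = 5/28 gives 0.251 and w = 1 gives 0.213. Full credit lowers the probability by 0.047; proportional credit lowers it by 0.009.

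**Sensitivity to history (15 to 30 mg, 1/3 at 15 mg, no early leaver).** One extra genuine non-DLT at 2, 4 or 8 mg gives 0.249, 0.241 or 0.229, so the step is allowed anyway.

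**Sensitivity to the prior.**
- Recentred on the stated medians: 15 to 30 mg is blocked both ways (0.328, 0.275). Four other steps flip: 2 to 4 (0.294 to 0.233), 4 to 8 (0.274 to 0.222), 8 to 15 (0.272 to 0.221) and 30 to 45 mg (0.268 to 0.215).
- Only the first mean shifted to logit(0.01): no step flips between 1/3 and 1/4.

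**Three enrolled, one early leaver (1/2 against 1/3, printed prior).** 4 to 8 mg moves from 0.308 to 0.247, 8 to 15 mg from 0.285 to 0.228, and 30 to 45 mg from 0.256 to 0.203. Here, leaving the patient out would open the replacement option rather than force a decision on 1/2.

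**The case against.** **The noncompliance sentence already removes these patients.** A patient who leaves on Day 6 for an unrelated reason misses most doses for reasons other than toxicity. On one reading that sentence makes the patient non-evaluable. So a reader who takes the DLT catch-all for the only safeguard goes further than the text allows. But it is unclear whether noncompliance covers a patient who has withdrawn, and if it does, it contradicts the exception. The conflict stands.

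**The patient is still observed.** A reader might infer that nobody watches the patient for the rest of Cycle 1. For someone who only stops treatment, that is not supported: the follow-up visit comes 30 ± 7 days after the decision, so a Day 6 stop is followed to about Day 29 to 43, and a related event within Cycle 1 could still be a DLT. However, 7.6.1 speaks of patients discontinued from the study, which under 8.2 includes follow-up procedures. The exception requires no observation in either case.

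**Trivial toxicity rarely leads to an omission.** Largely true. Table JZFA.7.2 ties suspension mainly to Grade 3 or 4 events and specified Grade 2 events. The exception has no grade limit, but a one-dose omission for minor toxicity is not the typical case.

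**The flip is close to the threshold and the model does not decide alone.** Both are true. Adverse events are the primary escalation criterion (7.1.1), and the team also weighs the observed DLT rate and may choose a smaller step. But the observed rate carries the same distortion: 1/4 is 25%, 1/3 is 33%.

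**No text says such a patient is DLT-free.** Correct. It is inferred from evaluable status and a binary model.

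**Conclusion.** The gap is real and its direction is anti-conservative. Followed as written, the exception gives full non-DLT credit without requiring exposure or observation, and a second sentence in the same section conflicts with it.

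Its size is modest and conditional. With the printed prior and 0/3 at all lower levels, one such patient takes two of six example steps across the 25% limit (0.260 to 0.213 and 0.287 to 0.226). In the histories checked, a crossing needs at least one DLT at the level. Which steps cross, if any, depends on the prior and the dosing history, and Appendix 7 raises the limit to 40% after Cohort 8.

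A reader might infer that one early leaver will generally unlock a blocked escalation. The documents do not support that: the prior is only an example, modest changes to it or to the history remove the 15 to 30 mg flip, and the team may hold the dose. The conclusion rests on the natural reading of the exception, on the absence of partial-follow-up weighting, and on the patient not being caught by the catch-all or the noncompliance sentence.

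**What to change.** Amend 7.6.1 to define the set that enters the N-CRM:

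- A patient counts as a non-DLT only with at least 80% of planned Cycle 1 doses, or with a toxicity-related shortfall and DLT observation to the end of Cycle 1, including post-treatment follow-up.
- An early leaver with a toxicity-related omission or reduction, no DLT and incomplete observation is reviewed by the investigator and sponsor. If not judged a DLT, the patient is left out of the model, may be replaced, and stays in all safety tables.
- State how the noncompliance sentence applies to withdrawn patients, so that it agrees with the exception.

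The cost is a short amendment and an occasional replacement patient. The review step still relies on judgment, but an unresolved case no longer counts as evidence of tolerability.
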